### **8.6. Prior and Concomitant Medications and Procedures**

All concomitant medications including prescription medications, over-the-counter preparations, growth factors, blood products, and parenteral nutrition taken during the 14 days before the date of enrollment, during the study treatment, and through 30 days after the last dose of study drug will be documented. Documentation will include information regarding start and stop dates, dose(s), and reasons for the medication use.

Administration of other concomitant nonprotocol anticancer therapies prior to progression is not permitted while on this study.

Administration of other concomitant investigational agents for any indication is not permitted while on this study.

Concomitant radiation therapy treatment for SCLC will be regarded as disease progression, and is not permitted while on this study.

Caution should be exercised when administering etoposide phosphate with drugs that are known to inhibit phosphatase activities (eg, levamisole hydrochloride). Although carboplatin has limited nephrotoxic potential, caution should be exercised when administering carboplatin with aminoglycosides, which has resulted in increased renal and/or audiologic toxicity. Any medication that is contraindicated when using etoposide or carboplatin is not permitted, and special warnings and precautions for use of carboplatin and etoposide should be observed.

Necessary supportive care such as antiemetics, antidiarrheals, etc., per the standard of care at the study center will be permitted. **Administration of hematopoietic growth factors in Cycle 1 will not be permitted (ie, no growth factors should be used prior to the actual Cycle 2 Day 1 dosing visit).** However, hematopoietic growth factors may be utilized in subsequent cycles at the investigator's discretion as stated in Section 8.4.4.2. To reduce potential immune system interactions, the use of dexamethasone as an antiemetic should be minimized where possible.

G1T28 is a time-dependent inhibitor of CYP3A4 and is a substrate for CYP3A4. G1T28 exposure may be altered by concomitant use of drugs that are strong CYP3A inhibitors or inducers. The exposure of drugs that are CYP3A substrates may be altered by concomitant use of G1T28 (Section 4.3.2).

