5. PRIMARY AND SECONDARY ENDPOINTS

The following general definitions will be applied to all endpoints derivation unless otherwise specified.

Term	Definition
Grade 4 neutropenia	ANC lab value that meets the common terminology criteria for adverse events (CTCAE) criteria for \geq Grade 4 toxicity
Grade 3/4 neutropenia	ANC lab value that meets the CTCAE criteria for \geq Grade 3 toxicity
Cycle baseline	The last non-missing value within the window starting from 3 days prior to the date/time of study drug administration on Day 1 of Cycle 1 and 1 day prior to Day 1 of each subsequent cycle (i.e. Cycle 2, Cycle 3, etc); must be prior to the time of study drug administration
Cycle NADIR	The lowest value for a given hematologic parameter that occurs between start of cycle and end of cycle and is less than the cycle baseline.
Duration of cycle	Total number of days from start of cycle to end of cycle, that is, date of end of a cycle - date of start of cycle + 1.
End of cycle*	Day 1 of the subsequent cycle. For example, the end of cycle for Cycle 1 is Day 1 of Cycle 2. For the last cycle (where no subsequent cycle is given), the end of cycle will be defined as Day 36.
Start of cycle	Day 1 of each cycle starts with the administration of study drug(s) (etoposide, carboplatin or trilaciclib)
Start of study	Day 1 of Cycle 1
Study baseline	The last non-missing value prior to, or on the date of administration of study drug(s) (etoposide, carboplatin or trilaciclib); must be prior to the time of study drug administration
Change from baseline	Calculated as the post-baseline value minus the baseline value. If the baseline value is missing for a particular endpoint, change from baseline will be missing.
Treatment period	Total number of days from start of cycle for Cycle 1 and end of cycle for the last cycle

* For various hematologic parameter analyses, the last assessment prior to end of cycle will be utilized in the analyses. Situations where this applies will be indicated as such.

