5.1. Efficacy endpoints

5.1.1. Primary Prospectively-Defined Clinical Endpoints for Efficacy

5.1.1.1. Febrile Neutropenia AEs

A cycle is considered to have a febrile neutropenia AE if any date between the start and stop date of the AE overlaps with any date between the start of cycle and end of cycle. If an event ends on the cycle start day, it will not be counted as an event in that cycle unless the event also started on that day. For the treatment period, the total number of febrile neutropenia AE events is the number of cycles where at least one febrile neutropenia AE is observed. If a patient did not have any febrile neutropenia AE events, the value of 0 will be assigned to that patient. AEs during the study is captured in the electronic database. The event terms are coded using the Medical Dictionary for Regulatory Affairs (MedDRA Version 20.1) and "FEBRILE NEUTROPENIA" is

a preferred term which can be used to identify the proper AE records. Data handling conventions for missing start and stop dates for AEs are described in [Section 5.2.1](#).

Any occurrence of a febrile neutropenia AE during the treatment period is defined as a binary variable (Yes or No); Yes if total number of febrile neutropenia AE events ≥ 1 is observed, No for other scenarios.

5.1.1.2. **RBC Transfusions**

Within a cycle, a RBC transfusion event is defined as either (1) an actual RBC transfusion, OR (2) eligible for RBC transfusion = hemoglobin < 8.0 g/dL. Therefore, for the treatment period, a total number of RBC transfusions (i.e. a RBC transfusion event = Yes) is obtained as the number of cycles in which there is at least one RBC transfusion event. If a patient did not have any RBC transfusion events, the value of 0 will be assigned to that patient. Hence, the total number of cycles without RBC transfusion is calculated as the total number of treatment cycles received – total number of cycles with RBC transfusion.

To define those cycles where a patient was eligible for a RBC transfusion, the lab value of hemoglobin (< 8.0 g/dL) must fall between start of cycle and end of cycle for that cycle. Any unscheduled data and the actual assessment date (rather than visit date) will be included in the derivation.

Hence, any occurrence of a RBC transfusion during the treatment period is defined as a binary variable (Yes or No); Yes if total number of cycles with RBC transfusion ≥ 1 is observed, No for other scenarios.

5.1.1.3. **Platelet Transfusions**

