Similarly, within a cycle, a platelet transfusion event is defined as either (1) an actual platelet transfusion, OR (2) eligible for platelet transfusion = platelet count $\leq 10 \times 10^9/L$. Therefore, for the treatment period, a total number of platelet transfusions (i.e. a platelet transfusion event = Yes) is the number of cycles in which there is at least one platelet transfusion event. If a patient did not have any platelet transfusion events, the value of 0 will be assigned to that patient. Therefore, the total number of cycles without a platelet transfusion is calculated as the total number of treatment cycles received – total number of cycles with platelet transfusion.

To define those cycles where a patient was eligible for a platelet transfusion, the lab value of platelet count ($\leq 10 \times 10^9/L$) must fall between start of cycle and end of cycle for that cycle. Any unscheduled data and the actual assessment date (rather than visit date) will be included in the derivation.

Hence, any occurrence of a platelet transfusion during the treatment period is defined as a binary variable (Yes or No); Yes if total number of cycles with platelet transfusion ≥ 1 is observed, No for other scenarios.

5.1.1.4. **GCSF Administrations**

Administration of GCSF is collected with the concomitant medications which are coded using World Health Organization Drug Dictionary (WHO-DD Version Sep2017). The criterion to select proper records is as follows: If the chemical subgroup from WHO-DD Version Sep2017 (i.e. TEXT4 for CODE4) takes value “COLONY STIMULATING FACTOR”, the medication is classified as GCSF.

A cycle where GCSF is administered concurrently will be identified by comparing the start and stop dates of each administration of GCSF to the start of cycle and end of cycle. If any of the dates of administration of GCSF overlap with any dates between the start of cycle and end of cycle, that cycle will be considered as having GCSF administered. Data handling conventions for missing start and stop dates are described in [Section 6.2.5](#).

For the treatment period, the total number GCSF administration is the number of cycles in which there is at least one GCSF dose administered. If a patient did not have any GCSF use, the value of 0 will be assigned to that patient. The number of cycles where GCSF was NOT given is calculated as total number of treatment cycles received – total number of cycles where GCSF was administered.

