5.2.7. Progression-free Survival

Since disease progression is assessed periodically, PD can occur any time in the time interval between the last assessment where PD was not documented and the assessment when PD is documented.

Hence, progression-free survival (PFS) is defined as the time (months) from date of first dose date of study drug for patients in Part 1 or date of randomization for patients in Part 2 until date of documented disease progression or death due to any cause, whichever comes first. More specifically, PFS will be determined using all the assessment data up until the last evaluable visit prior to or on the date of (i) disease progression as defined by RECIST 1.1 (Eisenhauer et al,

2009) or by clinical criteria (this will not apply to the BICR analysis); or (ii) withdrawal of consent; or (iii) receiving subsequent anti-cancer therapy, whichever is earlier.

PFS will be calculated using two response data sets: derived and BICR. For PFS determined by BICR, only progression per RECIST will be considered. For PFS as determined by derived, either clinical progression or progression by RECIST (whichever comes first) will be considered.

Death, regardless of cause, is always considered as a PD event. The detailed censoring rules for the analysis are summarized in [Table 18](#).

Table 18 Assignment of Progression or Censoring Based on Radiological Assessment

Situation	Date of Progression or Censoring	Outcome
No Baseline assessment	Date of first dose of study drug for patients in Part 1 or date of randomization for patients in Part 2	Censored
No progression	Date of last adequate radiological disease assessment	Censored
Treatment discontinuation for reasons other than disease progression	Date of last progression assessment with no documented progression	Censored
New anticancer treatment started prior to documented disease progression	Date of last adequate radiologic assessment no later than the initiation of new anticancer treatment	Censored
Disease progression	Date of the first reported progression	Progressed
Death without a PD	Date of death	Progressed
Investigator claim of clinical progression	Date of the investigator assigned PD	Progressed

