[c] Hematology may be obtained up to 3 days prior to first dose of G1T28/placebo + EP therapy in Cycle 1, and 1 day prior to first dose for subsequent cycles.

[d] Patient-reported outcomes should be completed at Days 1 and 10 of each cycle and at the Post-Treatment Visit. If a cycle is delayed, the patient should still complete the PRO on the scheduled Day 1 of the next cycle, as well as the actual first dosing day of the next cycle of G1T28 or placebo + E/P therapy. Patient-reported outcomes may be obtained up to 24 hours prior to the first dose of each cycle of G1T28 or placebo + E/P therapy.

[e] 60 ± 7 days after the post-treatment visit only for hematologic parameters and immunologic biomarker. The data is collected only for patients in Part 2.

[f] If Day 1 is included in the windowing, the associated assessment must be post G1T28 infusion.

Note: The end date of a cycle (EOC) is defined as the date of Day 1 study drug administration of its next cycle. For the last cycle (where no subsequent cycle is given), the end of cycle will be defined as Day 36 relative to the first dose of the cycle. Hence, for the last cycle, the window for EOC is 19-36.

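### The last cycle is scored to Day 36 with no cut at the start of subsequent anticancer therapy, so second-line hematologic events can count as outcomes of the randomized treatment

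*SAP*

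**What the plan says.** **The window.** SAP Section 5 opens its definitions table with "The following general definitions will be applied to all endpoints derivation unless otherwise specified". A cycle normally ends on Day 1 of the next one. For the final cycle the rule is "For the last cycle (where no subsequent cycle is given), the end of cycle will be defined as Day 36". The treatment period is then "Total number of days from start of cycle for Cycle 1 and end of cycle for the last cycle". The note to Table 20 (SAP 6.1.3) carries this into the laboratory windows: "Hence, for the last cycle, the window for EOC is 19-36".

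**What is scored inside it.** SAP 5.1.1.4 counts a cycle as having G-CSF on a date rule alone: "If any of the dates of administration of GCSF overlap with any dates between the start of cycle and end of cycle". Febrile neutropenia, ESA use, IV antibiotics and infection SAEs follow the same overlap logic. Transfusion endpoints also count laboratory eligibility, and SAP 5.1.1.2 adds: "Any unscheduled data and the actual assessment date (rather than visit date) will be included in the derivation". None of these rules asks whether the event is due to study treatment, and none stops at new therapy.

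**Neutropenia duration and MAHE.** In SAP 5.1.1.8 and 5.1.1.9 an episode resolves only if no later value below the threshold occurs before the end of the cycle. The early-stop rule there covers death, consent withdrawal and loss to follow-up, not new therapy. MAHE (SAP 5.1.1.11) censors event-free patients at the last assessment or contact.

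**Where a cut does exist.** For PFS (SAP 5.2.7) the list of stopping dates ends with "receiving subsequent anti-cancer therapy, whichever is earlier". Best overall response (SAP 5.2.6.4) has the same rule.

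**What the protocol allows.** Protocol 8.6: "Administration of other concomitant nonprotocol anticancer therapies prior to progression is not permitted while on this study". The bar lifts at progression.

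**The concern.** SAP Section 4 sets these endpoints up to show whether trilaciclib preserves the marrow under carboplatin and etoposide. A patient who progresses and moves to second-line treatment within the Day 36 window brings that regimen's G-CSF, transfusions, infections and low counts into the scored period. A single such event turns a binary endpoint to Yes, and one patient is 1/35 = 2.9 percentage points of an arm. Only patients who progress can be affected in this way, and their number and timing may differ between arms. Tumor outcome can therefore leak into what is meant to be a marrow comparison.

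**Working it through.** **1. The plan's own figure.** Protocol 13.1 and SAP 2.3 give precision for 35 patients per arm. The maximum Wilson half-width, z/(1+z²/n) × √(p(1−p)/n + z²/(4n²)) at p = 0.5, n = 35, z = 1.96, is 0.157. The t half-width, t(0.975, 34)/√35, is 0.344 SD. Both reproduce. They fix n = 35 per arm, but the documents give no event rates or dropout for these endpoints.

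**2. Where Day 36 comes from.** The next cycle is due on Day 22 and Protocol 6.1.3 allows up to 2 weeks of delay: 22 + 14 = Day 36. The last dose is on Day 3 and the Post-Treatment Visit is 30 to 33 days later (Protocol Table 9-1): Day 33 to Day 36. The length has a protocol basis.

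**3. Whether new therapy can start inside it.** Even-cycle scans are done within 7 days of the next cycle start (Protocol 6.1.5), so progression can be found around Day 15 to 22. I found no required interval before new therapy. That leaves up to about 14 days (36 − 22).

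**4. Whether the data would be captured.** Adverse events and concomitant medications are recorded to 30 days after the last dose (Protocol 8.6 and 11.3.1.6), which is Day 33. Hematology is drawn at the Post-Treatment Visit. SAP 6.1.3 starts the post-treatment window at the first dose date of the last cycle + 36, which is Day 37. An on-time visit on Day 33 to 36 therefore falls in the last cycle's end-of-cycle window.

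**5. Neutropenia duration: a worked case.** ANC is below 0.5 on Day 10, recovers on Day 15, and is below 0.5 again on Day 34 after new chemotherapy.
- Without the Day 34 value: 15 − 10 = 5 days, observed.
- With it: the episode never resolves, so it runs to the end of the cycle, 36 − 10 = 26 days, censored.

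With two or fewer durations SAP 5.1.1.8 uses the longest, so a patient who stops after Cycle 2 carries the 26 days into the analysis. It also meets the MAHE component for Grade 4 neutropenia longer than 5 days, which 5 days would not.

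**6. How many patients.** These fractions are assumptions: 10 to 30% of an arm stop for progression, half of those start new therapy in the window, and half of those have some hematologic event before Day 36.
- Share of an arm: c = 0.10 × 0.5 × 0.5 = 2.5% to 0.30 × 0.5 × 0.5 = 7.5%.
- Patients: 35 × c = 0.9 to 2.6.
- Patients already scored Yes cannot change. At an assumed 40% event rate, × 0.6 gives 0.5 to 1.6. At 20%, × 0.8 gives 0.7 to 2.1.

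**7. Effect on the comparison.** Assume 40% on placebo and 20% on trilaciclib, a difference of −0.200.
- Both arms equally affected: −0.200 × (1 − c) = −0.195 to −0.185, a shrinkage of 0.5 to 1.5 points.
- Placebo only: −0.200 − 0.6c = −0.215 to −0.245.
- Trilaciclib only: −0.200 + 0.8c = −0.180 to −0.140.

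For scale, the unadjusted 80% CI half-width is 1.2816 × √((0.4×0.6 + 0.2×0.8)/35) = 0.137.

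**8. Wider assumptions.** Let 5 to 40% of an arm start new therapy in the window, with a 10 to 50% chance of an event. The equal-contamination difference then runs from −0.199 to −0.160. With one arm affected it runs from −0.203 to −0.320 (placebo only) or −0.196 to −0.040 (trilaciclib only).

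**The case against.** The strongest reply is that the window is deliberate and the exposure narrow. Day 36 lets slow recovery in the last cycle count as it does in a cycle delayed by the permitted 2 weeks, and a fixed window is a defensible estimand choice. Patients who stop without progression, for example after six cycles, are barred from other anticancer therapy until they progress. After Day 22 the only further scheduled CBC before Day 36 is the Post-Treatment Visit, and the eligibility thresholds are strict (hemoglobin below 8.0 g/dL, platelets at or below 10 × 10⁹/L). Two MAHE components, treatment-related death and dose delay or reduction, are largely untouched. The sample size is set on clinical grounds and Protocol 13.2.3 calls the study descriptive. A cut has its own cost: early starters get fewer days in which to score Yes, and early starting depends on progression.

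Most of this stands and limits the size of the point. It does not remove it. The SAP states no rationale for treating the hematologic endpoints differently from response and PFS, and the duration rule misclassifies an affected patient whatever estimand was intended.

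A reader might infer more than the documents support:
- That second-line events have in fact been scored. The documents do not say how many patients start new therapy before Day 36.
- That 1 to 3 patients per arm, or 3 to 9 points, are misattributed on each endpoint. That follows only from rounding 0.9 to 2.6 up, treating the chance of any event as the chance for each endpoint, and ignoring patients already scored Yes.
- That Day 36 is itself wrong. Step 2 of the working shows its basis.

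**Conclusion.** The point holds in a limited, conditional form. For a patient who progresses and starts new therapy before Day 36, the SAP as written can score second-line events as outcomes of the randomized treatment and can turn a resolved 5-day Grade 4 episode into a censored 26-day one. The rule that would prevent this is already in the SAP for response and PFS.

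The size is unknown. The range of at most 2.5 to 7.5% of an arm rests entirely on the assumed fractions, and the comparison results also rest on the illustrative 40% and 20% rates. If early starts are equally common in both arms, the effect is small beside an 80% CI half-width of 13.7 points. If they are not, the difference can move in either direction; nothing in the documents says which. The change is worth making because it is cheap and removes a known misclassification, not because the documents show a material bias.

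**What to change.** Before unblinding, define the end of the last cycle as the earlier of Day 36 and the day before the first subsequent anticancer therapy, not counting prophylactic cranial irradiation given without progression. The exclusion is needed because Protocol 8.8 encourages that irradiation in responders, and SAP 6.2.6 classes any subsequent-therapy term containing the word RADIATION as radiotherapy. A cut at all radiotherapy would shorten the window for patients who have had no second-line treatment.

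Apply the definition to the treatment period, SAP 5.1.1.1 to 5.1.1.10 and the Table 20 end-of-cycle window. Add matching censoring at subsequent therapy to the MAHE rule in 5.1.1.11. Table 5 there counts a censored Grade 4 episode of 5 days or less as an event, so say whether an episode censored by the new cut also counts. Keep the fixed Day 36 analysis as a sensitivity analysis.

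Cost: a few sentences in the SAP and a date the PFS rule already needs; anticancer therapy details are collected under Protocol 10.7. The downside is a shorter and possibly informative last-cycle window for early starters. Comparing the two analyses shows how much that matters.

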- c Monthly phone calls will be made to each patient that is in the long-term Survival Follow-up Phase. Patients will be followed for survival until at least 50% of the patients in Part 2 have died. Any anticancer therapies used will be collected. In addition, blood samples for hematology and immunologic marker assessment will be collected at  $60 \pm 7$  days after the Post-Treatment Visit for patients in Part 2 only.
- d Informed consent may be obtained up to 28 days prior to the first study treatment administration.
- e Including medical, surgical, radiation history, smoking history, family history, documentation of tumor diagnosis, baseline signs and symptoms within 4 weeks prior to randomization, weight loss in the 6 months prior to randomization ( $\leq 5\%$  or  $> 5\%$ ), and medications taken within 14 days of enrollment.
- f Height will only be measured at the screening visit. Body surface area calculation (based on actual body weight) will be completed on Day 1 of each cycle and vital signs obtained immediately before and after G1T28 or placebo and E/P infusions. Vitals only need to be taken once between infusions.
- g Clinical chemistry will be obtained (albumin, alkaline phosphatase, total bilirubin, calcium, chloride, creatinine, glucose, inorganic phosphorus, potassium, total protein, ALT, AST, lactate dehydrogenase [LDH], sodium, and blood urea nitrogen [BUN]); see Section 11.3.2. Clinical chemistry and urine analysis may be obtained up to 72 hours prior to the first dose of each cycle of G1T28 or placebo + E/P therapy.
- h Hematology will be obtained (hemoglobin, hematocrit, WBCs with differential, and platelet counts); see Section 11.3.2. Hematology may be obtained up to 24 hours prior to first dose of each cycle of G1T28/placebo + EP therapy.
- i In Part 2 only, hematology will be collected at 60 days after the Post-Treatment Visit.
- j Patients participating in the Phase 1b dose-finding portion of Part 1 of the study, who have PK samples obtained, will have ECGs completed at the following time points on Days 1 and 3 of Cycle 1: predose, end of infusion (EOI) of G1T28, 2 hours ( $\pm 10$  minutes) after the start of G1T28, and 6.5 hours ( $\pm 15$  minutes) after the start of G1T28. The 2-hour ECG will be completed once the etoposide infusion is complete.

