3.1.1. Full Analysis Set

The full analysis set (FAS) includes all randomized patients who received at least 1 dose of study drug (etoposide, carboplatin, or trilaciclib). Analyses using the FAS will be conducted on the basis of the assigned treatment. All efficacy analyses will be assessed using the FAS. The FAS will be used for analyses of tumor response, progression-free survival (PFS) and overall survival (OS).

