3.1.2. Safety Analysis Set

The safety analysis set includes all enrolled patients who received at least 1 dose of study drug (etoposide, carboplatin, or trilaciclib). Analyses using the safety analysis set will be conducted on the basis of the actual treatment. All safety analyses will be assessed using the safety population.

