5.2.2. Vital Signs

Vital signs include pulse rate, respiratory rate, systolic blood pressure (SBP), diastolic blood pressure (DBP), weight, height (only measured at screening), and body temperature. Body Mass Index (BMI) will be computed as $\text{weight (kg)}/[\text{height (m)}]^2$, BSA will be computed using DuBois-DuBois formula as $0.20247 \times [\text{height (m)}]^{0.725} \times [\text{weight (kg)}]^{0.425}$.

For vital signs, change from baseline to each post-baseline visit and timepoint will be calculated. Vitals will be summarized by visit as collected and not windowed.

The potentially clinically significant findings of vital signs will also be defined based on criteria defined in [Table 11](#):

Table 11 Potentially Clinically Significant Criteria for Vital Signs

Vital Sign Parameter	Criterion value	Change from baseline
SBP	≥ 180 mmHg	Increase ≥ 40 mmHg
	≤ 90 mmHg	Decrease ≥ 40 mmHg
DBP	≥ 105 mmHg	Increase ≥ 20 mmHg
	≤ 50 mmHg	Decrease ≥ 20 mmHg
Pulse	≥ 120 bpm	Increase ≥ 40 bpm
	≤ 50 bpm	Decrease ≥ 40 bpm
Weight	n/a	Change $\geq 10\%$

bpm = beats per minute

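### The SAP's study-drug list omits placebo, so read literally the Part 2 vital-sign baseline falls before the blinded infusion on trilaciclib and after it on placebo

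*SAP*

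**What the plan says.** Four places in the SAP spell out the same list of study drugs, and a fifth (5.1.3.2, number of cycles received) repeats it.

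- Full analysis set (SAP 3.1.1): "all randomized patients who received at least 1 dose of study drug (etoposide, carboplatin, or trilaciclib".
- Safety analysis set (SAP 3.1.2): "includes all enrolled patients who received at least 1 dose of study drug (etoposide, carboplatin, or trilaciclib".
- Start of cycle (SAP 5, general definitions): "Day 1 of each cycle starts with the administration of study drug(s) (etoposide, carboplatin or trilaciclib".
- Study baseline (SAP 5, general definitions): "The last non-missing value prior to, or on the date of administration of study drug(s) (etoposide, carboplatin or trilaciclib", with the added condition that the value precede the time of administration, so clock time decides.

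The section 5 definitions apply to all endpoints unless something else is specified. SAP 5.2.2 specifies no other baseline for vital signs: "For vital signs, change from baseline to each post-baseline visit and timepoint will be calculated". Its Table 11 flags changes from baseline of at least 40 bpm in pulse, 40 mmHg in systolic and 20 mmHg in diastolic pressure.

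Protocol Table 9-1, footnote f (repeated under SAP Table 2), requires "vital signs obtained immediately before and after G1T28 or placebo and E/P infusions", with a single reading sufficing between infusions. Protocol 8.1 does not allow chemotherapy to start until the trilaciclib or placebo infusion is complete. Protocol 10.3 counts trilaciclib or placebo together with chemotherapy as the first dose, and lists the vital signs around the infusions among the postdose assessments.

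**The concern.** A baseline should be the same point in the patient's day in both arms. Here the definition starts the clock at the first listed drug. On trilaciclib that is the blinded infusion; on placebo it is the first chemotherapy infusion. A reading that the protocol treats as postdose becomes the placebo baseline.

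Safety and tolerability is the primary objective of Part 2. Protocol 4.3.4 names increased heart rate as a potential risk, seen in dogs as a rise of 30 to 60 bpm that resolved within a few hours. The reading just after the infusion is where such an effect would be sought, and the placebo arm is there to show what the infusion alone does.

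The same omission bears on analysis-set membership. A patient who receives trilaciclib and no chemotherapy is in the FAS and safety set; a patient who receives placebo and no chemotherapy is in neither.

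**Working it through.** The documents give no figure that this point turns on, so the check applies the SAP rule to a Cycle 1 Day 1 timeline.

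**Inputs.** The drug list and time rule come from SAP 5, the order of infusions from Protocol 8.1, and the vital-sign schedule from Protocol Table 9-1, footnote f. Clock times are assumed for illustration, in minutes from the start of the blinded infusion: infusions at 0 (trilaciclib or placebo), 34 (carboplatin) and 66 (etoposide); readings at -5, 32, 64 and 128. Only the order matters.

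**Step 1: baseline.** Let t0 be the start of the first listed drug. Baseline is the last reading before t0.

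| | Trilaciclib, as written | Placebo, as written | Placebo, with placebo listed |
|---|---|---|---|
| t0 | 0 | 34 | 0 |
| Baseline reading | -5 (before blinded infusion) | 32 (after blinded infusion) | -5 |
| Post-baseline readings that day | 32, 64, 128 | 64, 128 | 32, 64, 128 |

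As written, the trilaciclib arm has three post-baseline readings on Cycle 1 Day 1 and the placebo arm two. The missing one is the reading just after the blinded infusion. Adding placebo to the list makes the arms identical and leaves the trilaciclib arm unchanged.

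**Step 2: changes after the blinded infusion in later cycles.** Let s be the shift caused by the infusion itself in both arms, and e the drug effect, both measured from the pre-infusion value.

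- Trilaciclib change = s + e.
- Placebo change as written = s - s = 0; with the fix = s.
- Between-arm difference as written = s + e; with the fix = (s + e) - s = e.

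The error is therefore s. The documents give no value for s, so I assume -5, 0 and +5 mmHg:

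| s | e | Difference as written | Difference with the fix |
|---|---|---|---|
| -5 | 0 | -5 | 0 |
| -5 | 10 | 5 | 10 |
| 0 | 0 | 0 | 0 |
| 0 | 10 | 10 | 10 |
| +5 | 0 | 5 | 0 |
| +5 | 10 | 15 | 10 |

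If s = 0 there is no error in these comparisons.

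**Step 3: change-based flags.** In the placebo arm, a value X above the pre-infusion level is flagged as an increase when X - s reaches the threshold, that is, when X reaches the threshold plus s. For systolic pressure the effective threshold is 40 - 5 = 35 or 40 + 5 = 45 mmHg, against 40 on trilaciclib. For diastolic it is 20 - 5 = 15 or 20 + 5 = 25, against 20. The placebo arm also has one fewer Cycle 1 Day 1 reading that can raise a flag.

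**Step 4: analysis sets and dates.** Membership of the FAS and safety set changes only for a placebo patient who received the blinded infusion and no chemotherapy. Start-of-cycle dates change only if placebo and the first chemotherapy fall on different dates; Protocol 8.1 limits the gap to 4 hours. Scheduled Day 1 laboratory samples precede dosing (Protocol 10.3), so laboratory baselines are barely touched.

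**The case against.** The strongest reply is that trilaciclib in these lists is shorthand for the blinded infusion. SAP 6.2.7.3 summarizes dose modification for the same three drugs, and SAP 6.2.8.1 and Table 5 use the same list for relatedness of adverse events and deaths. In Part 2 the investigator is blinded (Protocol 8.5), so attribution to trilaciclib there can only mean attribution to the blinded infusion. The Part 2 schema note likewise names only G1T28 though it covers both arms. With Protocol 10.3 labelling the between-infusion reading postdose, a sensible programmer would not use it as a baseline.

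Much of this stands: the intent is very probably symmetric. But the SAP does not say so. It sets trilaciclib against placebo when comparing arms (6.2.7, 6.2.7.1). In notes to Table 20 it writes G1T28/placebo or G1T28 or placebo when it means either infusion, yet note [f] to that table says only G1T28. SAP 7 does not list the omission as a deliberate change. SAP 6.1.1 requires outputs to be checked for consistency with the plan, so a literal reading is a real possibility.

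The reply is also right about impact. A reader might infer that the comparison of infusion effects is lost. It is not. SAP 6.2.8.3 tabulates observed values as well as changes. Infusion-reaction events are selected by calendar date (SAP 5.2.1). Later-cycle post-infusion changes exist in both arms, though with unequal baselines. The absolute limits in Table 11 use no baseline, provided its two columns are separate criteria, which the SAP does not state. A heart-rate rise on trilaciclib would still show against that arm's own pre-infusion baseline. Phase 1a reported no significant vital-sign changes (Protocol 4.2), and nothing in the documents shows that the placebo infusion shifts vital signs.

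Nor should a reader infer that the placebo arm drops out of the FAS or safety set: any placebo patient given chemotherapy qualifies through a listed drug.

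**Conclusion.** Wrong as written, and minor. The operative list omits placebo in five SAP definitions and conflicts with the protocol's account of the first dose. Followed literally, it gives arm-dependent vital-sign baselines, removes the placebo arm's Cycle 1 Day 1 post-infusion change, and puts the change-based pulse and blood-pressure flags on different reference points.

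In principle this reaches every placebo patient with a between-infusion reading, 35 as planned. Its numerical size equals the unknown infusion shift s and is zero if s is zero. The analysis-set asymmetry is probably 0 to 1 patients, a judgement rather than a documented figure. Safety summaries are descriptive (SAP 6.2.8), and no planned efficacy comparison is materially affected.

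The conclusion assumes that the definition is programmed as worded and that the between-infusion reading is recorded before chemotherapy starts.

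**What to change.** Write *etoposide, carboplatin, or trilaciclib/placebo* in SAP 3.1.1, 3.1.2, the start-of-cycle and study-baseline definitions in section 5, and 5.1.3.2. In Table 20, note [f], write *post G1T28/placebo infusion*. State that study baseline and cycle baseline are the last values before the start of the first infusion of the day, blinded infusion included.

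The cost is a few words. No new data are needed: Protocol 8.9 already has sites record start and end times of every infusion, placebo included. The change should be made before unblinding; if that point has passed, the clinical study report should say which anchor was programmed.
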